ECG (standard 12-lead)	X	X	X	X	X	X		X	X	X	X	X			
 At screening: single 12-lead ECG. Cycles 1 to 3: triplicate 12-lead ECGs to determine mean QTcF interval. For the days of dose administration, perform ECG up to 60 minutes prior to dosing (SC or IV), and at the end of infusion (IV only). From Cycle 4 onwards: Triplicate 12-lead ECG up to 60 minutes prior to dosing on Day 1 of every 3 cycles (C4D1, C7D1, etc.). Refer to Section 8.2.3 for additional information.
Study Intervention															
PF-07260437 administration			X				X		X		X				
 Full dose at every dosing timepoint.

Table 1. Study Schedule of Assessments – Part 1 Without Priming

[figure not shown]
Visit Identifier Abbreviations used in this table may be found in Appendix 17	Screening	Treatment Period										EOT	4-week Follow- up	90-day Follow- up for irAEs	Notes
		Cycle 1 = 28 days					Cycle ≥2 (28 days)								
Study Day	-28 to -1	1	2	3 ^a	8	15 ^a	22	1	C3D8 ^b	15					
Visit Window (days)		±2			±2	±2	±2	±2	±2	±2		±7		±7	
 Additional visit window may be allowed after discussion and agreement between investigator and sponsor. a. End of inpatient observation (PK, ECG, vital signs). b. PK/PD and ECG only.
Premedication		(X)			(X)		(X)		(X)						
 Prophylactic premedication is not allowed during the DLT evaluation period during initial dose escalation. However, if the participant experiences an infusion related reaction (IV), allergic reaction, significant injection site reaction, CRS, fever/chills, allergic reaction, nausea/vomiting, hypotension, or pain, appropriate treatment should initiate and premedication as prophylaxis may be considered for subsequent injections as well as for new participants. See Section 6.1.1.1 for additional information.
Concomitant therapy															
 Include medications given to treat AEs, chronic conditions, and supportive medications (except premedication). See Section 6.8 for additional information.

Table 1. Study Schedule of Assessments – Part 1 Without Priming

Visit Identifier Abbreviations used in this table may be found in Appendix 17	Screening	Treatment Period										EOT	4-week Follow- up	90-day Follow- up for irAEs	Notes
		Cycle 1 = 28 days					Cycle ≥2 (28 days)								
Study Day	-28 to -1	1	2	3 ^a	8	15 ^a	22	1	C3D8 ^b	15					

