Serious and nonserious AE monitoring		◀ →													
 See Sections 8.2 and Section 8.3.

Table 1. Study Schedule of Assessments – Part 1 Without Priming

Visit Identifier Abbreviations used in this table may be found in Appendix 17	Screening	Treatment Period										EOT	4-week Follow- up	90-day Follow- up for irAEs	Notes
		Cycle 1 = 28 days					Cycle ≥2 (28 days)								
Study Day	-28 to -1	1	2	3 ^a	8	15 ^a	22	1	C3D8 ^b	15					
Visit Window (days)		±2			±2	±2	±2	±2	±2	±2		±7		±7	
Clinical Safety Laboratory Assessments															
Hematology	X	X	X		X	X	X	X		X	X	X			
Blood chemistry	X	X	X		X	X	X	X		X	X	X			
Coagulation	X	Every 8 weeks from C1D1								X					
Lipase and amylase		X						X			X				
TSH and free T4	X														

- Additional visit window may be allowed after discussion and agreement between investigator and sponsor.
- a. End of inpatient observation (PK, ECG, vital signs).
- b. PK/PD and ECG only.
- See [Section 8.2.4](#).
- See [Appendix 2](#) for a list of Clinical Laboratory tests to be done.
- No need to repeat on C1D1 if screening was performed within 7 prior days. All samples will be collected prior to dosing.
- No need to repeat on C1D1 if screening was performed within 7 prior days.
- TSH WNL for institution; in participants with abnormal TSH, if free T4 is WNL and participant is clinically euthyroid, participant is eligible.

Table 1. Study Schedule of Assessments – Part 1 Without Priming

Visit Identifier Abbreviations used in this table may be found in Appendix 17	Screening	Treatment Period										EOT	4-week Follow- up	90-day Follow- up for irAEs	Notes
		Cycle 1 = 28 days					Cycle ≥2 (28 days)								
Study Day	-28 to -1	1	2	3 ^a	8	15 ^a	22	1	C3D8 ^b	15					
Visit Window (days)		±2			±2	±2	±2	±2	±2	±2		±7		±7	
 Additional visit window may be allowed after discussion and agreement between investigator and sponsor. a. End of inpatient observation (PK, ECG, vital signs). b. PK/PD and ECG only.
Viral disease screen	X														
 Include HBsAg, HBcAb, and HCV antibody. In the case of apparent ongoing HBV or HCV infection, reflex serum DNA or RNA viral load testing, respectively, will be performed. See Appendix 2 for additional information.

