Visit Identifier Abbreviations used in this table may be found in Appendix 17	Screening	Treatment Period									EOT	4-week Follow- up	90-day Follow- up for irAEs	Notes
		Cycle 1 =28 days				Cycle ≥ 2 (28 days)								
Study Day	-28 to -1	1	2 ^a	8	15	16 ^a	22	1	8 ^b	15				
 Additional visit window may be allowed after discussion and agreement between investigator and sponsor. 
a: End of inpatient observation (PK, ECG, vital signs).
 
b: This D8 visit is only applicable for Cycles 2 and 3, whereas, C3D8 is applicable for PK/PD and ECG only.

Visit Window (days)		± 2		± 2	± 2			± 2	± 2	± 2		± 7	± 7	
Study Intervention														
PF-07260437		X (priming dose)		(X ^c)	X			X		X				
 C1D1 is priming dose and C1D15 is full/maintenance dose. c: A 2-step priming may be considered on C1D1 and C1D8. See Section 4.1 for additional information.

Table 3. Study Schedule of Assessments – Part 1 With Priming

Visit Identifier Abbreviations used in this table may be found in Appendix 17	Screening	Treatment Period									EOT	4-week Follow- up	90-day Follow- up for irAEs	Notes
		Cycle 1 =28 days												
Study Day	-28 to -1	1	2 ^a	8	15	16 ^a	22	1	8 ^b	15				
 Additional visit window may be allowed after discussion and agreement between investigator and sponsor.
Visit Window (days)		±2	±2	±2		±2	±2	±2	±2	±2		±7	±7	
a: End of inpatient observation (PK, ECG, vital signs).
 
b: This D8 visit is only applicable for Cycles 2 and 3, whereas, C3D8 is applicable for PK/PD and ECG only.

Premedication		(X)	(X ^d)	(X)			(X)		(X)					
 Prophylactic premedication is not allowed during the DLT evaluation period during initial dose escalation. However, if the participant experiences an infusion related reaction (IV), allergic reaction, significant injection site reaction, CRS, fever/chills, allergic reaction, nausea/vomiting, hypotension, or pain, appropriate treatment should initiate and premedication as prophylaxis may be considered for subsequent injections as well as for new participants. See Section 6.1.1.1 for additional information. d: Only applicable to 2-step priming

Table 3. Study Schedule of Assessments – Part 1 With Priming

Visit Identifier Abbreviations used in this table may be found in Appendix 17	Screening	Treatment Period									EOT	4-week Follow- up	90-day Follow- up for irAEs	Notes

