Visit Window (days)		±2		±2	±2		±2	±2	±2	±2		±7	±7	
a: End of inpatient observation (PK, ECG, vital signs).
 
b: This D8 visit is only applicable for Cycles 2 and 3, whereas, C3D8 is applicable for PK/PD and ECG only.

Injection site tolerability assessment		X	X	X				As clinically indicated						
 C1D1: at least 1 hour and 24 hours (±1 hr) after injection. C1D15: at least 1 hour after injection. See Section 8.2.6 for additional information
Efficacy Assessment														
Tumor response assessment	X	Performed every 8 weeks from C1D1 (±7 days) for the first 6 months, every 12 weeks (±7 days) for the next 18 months, and every 4 months thereafter.							X					
 CT/MRI scans of head, chest, abdomen, pelvis, any clinically indicated sites of disease (see Section 8.1.1).
Bone Scan or PET	X	Performed every 8 weeks from C1D1 (±7 days) for the first 6 months, every 12 weeks (±7 days) for the next 18 months, and every 4 months thereafter.							X					
 For bone metastasis (see Section 8.1.1).
Safety Assessment														
Serious and nonserious AE monitoring		↔												
 See Sections 8.2 and Section 8.3.
Clinical Safety Laboratory Assessments														
														
 See Section 8.2.4 See Appendix 2 for a list of Clinical Laboratory tests to be done.

Table 3. Study Schedule of Assessments – Part 1 With Priming

Visit Identifier Abbreviations used in this table may be found in Appendix 17	Screening	Treatment Period									EOT	4-week Follow- up	90-day Follow- up for irAEs	Notes
		Cycle 1 =28 days												
Study Day	-28 to -1	1	2 ^a	8	15	16 ^a	22	1	8 ^b	15				
 Additional visit window may be allowed after discussion and agreement between investigator and sponsor.
Visit Window (days)		±2		±2	±2		±2	±2	±2	±2		±7	±7	
a: End of inpatient observation (PK, ECG, vital signs). b: This D8 visit is only applicable for Cycles 2 and 3, whereas, C3D8 is applicable for PK/PD and ECG only.

Hematology	X	X		X	X		X	X	X (C2 only)	X	X	X		
 No need to repeat on C1D1 if screening was performed within 7 prior days. All samples will be collected prior to dosing.
Blood Chemistry	X	X		X	X		X	X	X (C2 only)		X	X		

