2.2.3. Nonclinical Safety

PF-07260437 was characterized in toxicity studies up to 1 month in duration in cynomolgus monkeys (ie, the only pharmacologically relevant species). The highest doses tested in the 1-month study (0.3 mg/kg/week SC and 0.1 mg/kg/week IV) are the HNSTDs and NOAELs. A more conservative MABEL approach was used instead of the 1/6 HNSTD calculation to select the clinical starting dose. For more information about the clinical starting dose, see [Section 4.3.1](#).

Based on the nonclinical toxicity studies, the organs of potential clinical importance are the immune system and pancreas. The key findings were immune-mediated effects from the primary pharmacology of PF-07260437 (ie, cytokine induction and T cell activation). CRS-like clinical observations included emesis, hypoactivity, and reduced appetite. Mild to moderate increases of circulating cytokines were mostly observed after the first dose, typically peaked by 7 hours, and returned to baseline values within 48 hours. Immune-related toxicities (eg, mononuclear cell infiltration, vacuolation, and degeneration) in tissues with B7-H4 expression were typically minimal to mild in severity and fully or partially resolved after a recovery period. There were no findings in the pancreas; however, expression of B7-H4 in human pancreas may result in inflammation not observed in cynomolgus monkeys due to lack of expression of B7-H4 in the latter. Given this, the pancreas has been included as a potential target organ.

Overall, the nonclinical toxicity of PF-07260437 caused pharmacology-based, exposure-responsive findings expected to be reversible and clinically monitorable.

More details of the nonclinical safety program are provided in the IB.

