Participants in Part 2 will receive PF-07260437 at the RDE (with or without priming, based on results from Part 1). Depending on the evaluation of safety and PK data of the priming dose cohorts, Part 2 participants may be switched to a priming dose schedule determined from Part 1 dose escalation with priming. All Part 2 participants will be observed inpatient for at least 24 hours after the first SC dose on C1D1, and if a priming dose approach is used, participants will be observed for up to 24 hours after the first full dose on C1D15 (observation after additional priming doses if given will be based on emerging data). Participants may only be released after the investigator has confirmed the participant has not exhibited signs of CRS (Table 7).

Table 7. Inpatient Observation Stays for SC Administration

Part	Schedule	C1D1	C1D15	All other outpatient visits
1	Without Priming	Up to 48 hours	8 hours	1 hour
	With Priming	24 hours	24 hours	1 hour
2	With or Without Priming	24 hours	24 hours if priming is used; 8 hours without priming	At investigator's discretion

*The length and number of inpatient observation stays may be modified based on emerging data but in any case, participants may only be released after confirmation of the absence of clinically significant CRS.

If the 2 (or more) step-up priming doses approach is implemented, the observation period after the second priming SC dose on C1D8 will be determined based on emerging safety data and clinical investigator's assessment.

Please refer to [Section 6.1](#) for general recommendation on inpatient observation stays for SC and IV administration as applicable.

Modification of inpatient observation period might be allowed based on emerging safety data and will require discussion and agreement between investigator and sponsor.

All participants will be required to provide archival FFPE material containing tumor that is of diagnostic quality and representative of their diagnosed malignancy or consent to undergo a fresh biopsy during screening for both Part 1 dose escalation and Part 2 dose expansion. For 5 participants in each of Part 2A and 2C and for 5 HR+ HER2- BrCa participants and 5 TNBC participants in Part 2B, paired pre- and on-treatment biopsy samples will be mandatory. These biopsies will be to confirm the MoA, understand tumor-based pharmacodynamics and evaluate potential resistance mechanism during treatment.

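### Part 1 primed participants have no scheduled hematology, chemistry or brief examination 24 hours after the priming dose or the first full dose; unprimed participants do after their first full dose

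*Protocol*

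**What the plan says.** **Unprimed (Protocol 1.3.1, Table 1).** The dosing note reads "Full dose at every dosing timepoint", so C1D1 is the first full dose. Hematology, blood chemistry and brief physical examination are all marked on C1D2. The laboratory note reads "No need to repeat on C1D1 if screening was performed within 7 prior days. All samples will be collected prior to dosing".

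**Primed (Protocol 1.3.2, Table 3).** The dosing note reads "C1D1 is priming dose and C1D15 is full/maintenance dose". Hematology, chemistry and brief physical examination are marked on C1D1, D8, D15 and D22, and are blank on D2 and D16. Footnote a describes the D2 and D16 visits as the end of inpatient observation, with PK, ECG and vital signs. The same pre-dose rule applies: "All samples will be collected prior to dosing".

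**How the results are used.** Laboratory abnormalities are a primary endpoint (Section 3) and are summarized by worst grade observed (Protocol 9.3.5.3, SAP 6.1.3). Grade 4 neutropenia, thrombocytopenia and anemia are DLTs with no minimum duration (4.3.6.1). The primed DLT window counts laboratory results up to Day 43, which is C2D15 (4.3.6).

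**The concern.** The two regimens do not have the same scheduled chance of showing an early laboratory toxicity. A DLT rate or a worst-grade table depends on when blood is drawn. If one regimen is sampled at 24 hours and the other is not, a difference between them can reflect the sampling rather than the drug.

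The gap also falls in an awkward place. One trigger for priming is recurrent Grade ≥2 CRS (4.1), so the regimen without 24-hour laboratory tests may be the one adopted after acute toxicity has been seen. The risk table in 2.3.1 lists frequent safety laboratory tests among the CRS mitigations.

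The dose-escalation model does not correct for this. Section 9.3.2 takes account of the different lengths of the DLT windows, but not of different sampling within them. The prior for the primed model is derived from the unprimed data by a MAP approach. A hierarchical prior allows for differences between data sources in general. It cannot tell fewer DLTs from fewer detected DLTs.

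**Working it through.** The plan states no figure to reproduce, so the check sets the two schedules side by side. In all six rows the cells line up with the column headings: the Cycle 2-only entry in Table 3 falls under Day 8, and the vital-signs row is marked on D2 and D16, as footnote a requires.

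| Assessment | Unprimed, Table 1 | Primed, Table 3 |
|---|---|---|
| Hematology, Cycle 1 | D1, **D2**, D8, D15, D22 | D1, D8, D15, D22 |
| Chemistry, Cycle 1 | D1, **D2**, D8, D15, D22 | D1, D8, D15, D22 |
| Brief examination, Cycle 1 | D1, **D2**, D8, D15, D22 | D1, D8, D15, D22 |
| Hematology, Cycle ≥2 | D1, D15 | D1, D8 (Cycle 2 only), D15 |
| Chemistry, Cycle ≥2 | D1, D15 | D1, D8 (Cycle 2 only); **D15 blank** |

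**Days after the first full dose** (study day minus 1 unprimed, minus 15 primed; C2D1 = Day 29, C2D8 = Day 36, C2D15 = Day 43):

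- Unprimed hematology and chemistry: 2−1 = 1, 8−1 = 7, 15−1 = 14, 22−1 = 21, 29−1 = 28. Five time points.
- Primed hematology: 22−15 = 7, 29−15 = 14, 36−15 = 21, 43−15 = 28. Four time points.
- Primed chemistry: 7, 14 and 21 only, because C2D15 is blank. Three time points.

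**First result after each primed dose.** After the priming dose it is 8−1 = 7 days. After the first full dose it is 22−15 = 7 days. With the ±2-day window on D22 and a dose given on Day 15, the range is 20−15 = 5 to 24−15 = 9 days.

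**Count over each whole DLT window, after the first dose.**

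- Unprimed, 28 days: D2, D8, D15, D22 and D29, giving 5 for both hematology and chemistry.
- Primed, 42 days: D8, D15, D22, D29, D36 and D43, giving 6 for hematology. Chemistry has 5, because Day 43 is blank.

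**Direction.** Take an abnormality that is present at 24 hours and has resolved by the next scheduled sample. Unprimed participants have one scheduled sample while it is present; primed participants have none. A worst observed grade is a maximum over samples, so an added time point can leave it unchanged or raise it but cannot lower it. The omission can therefore only reduce scheduled detection under priming.

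**Day 43.** The example window in 4.3.6 is 14 + 28 = 42 days, with laboratory results on the morning of Day 43; C2D15 is 28 + 15 = 43. Table 3 marks hematology there but not chemistry, so the two places disagree.

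**The case against.** The case on the other side has several parts, and most of them limit the point.

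- **Primed participants are not measured less overall.** Table 3 adds a C2D8 laboratory visit that Table 1 lacks, and scheduled hematology over the DLT window is 6 against 5. This stands. The gap concerns the 24-hour time point, not total sampling.
- **The pattern may be deliberate.** The end-of-observation visit carries only PK, ECG and vital signs in both regimens (D3 unprimed, D2 and D16 primed), and unprimed D2 falls in the middle of a 48-hour stay. Unprimed participants also have no 24-hour laboratory test after their second dose. This may explain how the difference arose, but the protocol gives no reason for it.
- **Other safeguards exist.** Primed participants are under inpatient observation for 24 hours after both doses, and 8.2.4 allows unscheduled tests. This stands for symptomatic events. The tests are permitted rather than required, and a silent event would not prompt one.
- **Many brief laboratory events are not DLTs.** Section 4.3.6.3 excludes isolated Grade 3 abnormalities without sequelae that are corrected within 72 hours. This stands, and it narrows the DLT issue mainly to silent Grade 4 cytopenia.

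A reader might infer that early toxicity is generally gone within two days, so that a 7-day sample would miss most of it. Section 2.2.3 does say that levels "typically peaked by 7 hours, and returned to baseline values within 48 hours", but this describes circulating cytokines in monkeys. It says nothing about how long cytopenias or transaminase rises last in patients.

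A reader might also infer that a planned primed-versus-unprimed comparison is biased. Section 4.1 says "Depending on the evaluation of safety and PK data of the priming dose cohorts, Part 2 participants may be switched", which refers to the primed cohorts' own data. Posteriors are evaluated separately by regimen, there is no hypothesis testing, and no cross-regimen laboratory table is planned. Part 2 uses one schedule (Table 5) for both regimens, so this Part 1 difference does not carry over to it.

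**Conclusion.** The schedule difference is real and unexplained. In Part 1, unprimed participants have scheduled hematology, chemistry and a brief examination about 24 hours after the first full dose. Primed participants have none at 24 hours after either the priming dose or the first full dose, and wait about 7 days in each case.

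The consequence is limited to abnormalities that are transient and clinically silent: present at 24 hours and gone by about day 7. Grade 4 cytopenia matters most, because it is a DLT of any duration. For these events the direction is under-ascertainment in the primed regimen. Persistent abnormalities would appear at D8 or D22, and symptomatic ones could prompt unscheduled tests.

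No percentage of missed events should be attached to this. A figure would need the frequency, onset and duration of such abnormalities in patients. The documents give none of these, and Section 2.2.4 confirms that there are no clinical data. Nor do the documents support saying that priming will look safer overall or that the choice of RDE will change. The point is worth acting on because the gap is specific, it bears on primary endpoints, and it is cheap to close.

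**What to change.** In Table 3, mark hematology, blood chemistry and brief physical examination on C1D2 and C1D16, and extend footnote a to match. Take the samples with the 24-hour PK and cytokine draws that Table 4 already schedules after both doses. If the sponsor prefers to keep the present schedule, the protocol should give the reason.

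Separately, reconcile the blank chemistry cell at Cycle ≥2 Day 15 in Table 3 with Section 4.3.6, which counts laboratory results from Day 43 (C2D15) in the primed DLT window.

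Unprimed Day 2 results should stay in the safety summaries. They are valid safety data, and removing them would only hide information.

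The cost is a schedule amendment, two extra routine tube sets and two brief examinations per primed participant, all during existing inpatient observation. No new visit or separate blood draw is needed.

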1.3.2.1. Part 1 - PK, Immunogenicity, PD, Biomarker, and Biospecimen – With Priming

Table 4. PK, Immunogenicity, PD, Biomarker, and Biospecimen Schedule of Assessments – Part 1- With Priming

Visit Identifier Abbreviations used in this table may be found in Appendix 16	Screenin g	CYCLE 1 - A CYCLE 2 - B CYCLE 3 - C CYCLE \geq 4 - D										EOT	Notes		
		Day 1				Da y 2	Day 8	Day 15							
		Pre (0)	1 hr	4 hr	8 hr	24 hr	168 hr	Pre (0)	1 hr	4 hr	8 hr	24 hr	168 hr		
Hours Before/After Dose		-6 hr	+ 10 min	\pm 30 min	\pm 1 hr	\pm 3	\pm 24 hr	-6 hr	\pm 10 min	\pm 30 mi n	\pm 1 hr	\pm 3 hr	\pm 24 hr		
 Pre-dose samples: hours before the immediate dose Post-dose samples: hours after the most recent scheduled dose
PK Assessments															
PK blood sampling		A, B, C, D	A, C (IV only)	A, C	A, C	A	A, C	A, C	A (IV only)	A	A	A	A	X	
 If CRS is suspected, additional PK sample should be collected at time of AE occurrence if not already scheduled IV only: if actual duration of infusion differs from 1 hour, 1-hour point should be adjusted for the sample to be collected at the end of infusion. See Section 8.4 for additional information.
Immunogenicity Assessments															
Blood samples for ADA and NAb		A, B, C, D											X	
 From Cycle 4 onwards: collection on Day 1 of 	

Table 4. PK, Immunogenicity, PD, Biomarker, and Biospecimen Schedule of Assessments – Part 1- With Priming

Visit Identifier Abbreviations used in this table may be found in Appendix 16	Screenin g	CYCLE 1 - A CYCLE 2 - B CYCLE 3 - C CYCLE ≥4 - D										EOT	Notes		
		Day 1				Da y 2	Day 8	Day 15							
		Pre (0)	1 hr	4 hr	8 hr	24 hr	168 hr	Pre (0)	1 hr	4 hr	8 hr	24 hr	168 hr		
Hours Before/After Dose		-6 hr	+ 10 min	± 30 min	±1 hr	±3 hr	±24 hr	-6 hr	± 10 min	± 30 mi n	±1 hr	±3 hr	±24 hr		
 Pre-dose samples: hours before the immediate dose Post-dose samples: hours after the most recent scheduled dose
Visit Window														every 3 cycles. (C4D1, C7D1 etc.) • See Section 8.7 for additional information.	
Pharmacodynamic and Biomarker Samples															
Soluble B7-H4 blood sample		A, B, C, D		A, C	A,C	A	A,C	A,C		A	A	A	A	X	
 From Cycle 4 onwards: collection on Day 1 of every 3 cycles (C4D1, C7D1, etc.) See Section 8.6.6 for additional information.
Serum for cytokine and circulating markers (central lab)		A, B	A	A	A	A	A	A	A	A	A	A	A		• Refer to Section 8.6.3 .
Blood sample for immunophenotyp ing		A, B				A	A	A			A	A			• Refer Section 8.6.4 .

Table 4. PK, Immunogenicity, PD, Biomarker, and Biospecimen Schedule of Assessments – Part 1- With Priming

Visit Identifier Abbreviations used in this table may be found in Appendix 16	Screenin g	CYCLE 1 - A CYCLE 2 - B CYCLE 3 - C CYCLE ≥4 - D										EOT	Notes		
		Day 1				Da y 2	Day 8	Day 15							
		Pre (0)	1 hr	4 hr	8 hr	24 hr	168 hr	Pre (0)	1 hr	4 hr	8 hr	24 hr	168 hr		
Hours Before/After Dose		-6 hr	+ 10 min	± 30 min	±1 hr	±3 hr	±24 hr	-6 hr	± 10 min	± 30 mi n	±1 hr	±3 hr	±24 hr		
 Pre-dose samples: hours before the immediate dose Post-dose samples: hours after the most recent scheduled dose
Visit Window															
Mandatory archival tumor tissue	X													
 All participants must provide archival tissue. Must refer to Section 8.6.1 for specific instruction/acceptable tissues samples. 	
Optional de novo pre-dose and paired on- treatment biopsy	(X)							(B)					(X)	
 (B) and (X) = Optional. Must refer to Section 8.6.1 for specific instruction/acceptable tissues samples. 	
Plasma sample for cell free DNA analysis		A											X	
 Refer to Section 8.6.3. A: 10 mL-blood specimens optimized for plasma preparation will be collected. 	
Blood for germline subtraction		A												
 2 mL whole blood sample will be collected and sequenced along with tumor samples enabling subtraction of germline 	

PFIZER CONFIDENTIAL

CT02-GSOP Oncology Clinical Protocol Template (01 March 2021)

Page 51

Table 4. PK, Immunogenicity, PD, Biomarker, and Biospecimen Schedule of Assessments – Part 1- With Priming

Visit Identifier Abbreviations used in this table may be found in Appendix 16	Screenin g	CYCLE 1 - A CYCLE 2 - B CYCLE 3 - C CYCLE ≥4 - D										EOT	Notes		
		Day 1				Da y 2	Day 8	Day 15							
		Pre (0)	1 hr	4 hr	8 hr	24 hr	168 hr	Pre (0)	1 hr	4 hr	8 hr	24 hr	168 hr		
Hours Before/After Dose		-6 hr	+ 10 min	± 30 min	±1 hr	±3 hr	±24 hr	-6 hr	± 10 min	± 30 mi n	±1 hr	±3 hr	±24 hr		
 Pre-dose samples: hours before the immediate dose Post-dose samples: hours after the most recent scheduled dose
Visit Window														variations from somatic mutations.	
Retained Research Sample for Genetics [Prep D1]		A												
 A 4 mL whole blood sample optimized for DNA isolation Prep D1 will be collected. See Laboratory Manual - Retained Research Sample collection. Prep D1 Retained Research Samples for Genetics: If not collected on the designated collection day, collect at the next available time point when biospecimens are being collected in conjunction with a participant visit. See Section 8.5.2 for additional information. 	

